#### **11.5 Reporting of Serious Adverse Events**

Participants will be asked to contact the study site immediately in the event of any serious adverse event. Research sites will be asked to contact NCTU immediately (within 24 hours) upon becoming aware of any serious adverse event as described in section 11.2.

Following identification of an SAE, sites will email completed (or partially completed) SAE Form to central coordinating team at the NCTU within 24 hours of becoming aware of the SAE. The investigator (or delegate) must complete, date and sign an SAE form.

Sites will report an SAE by emailing the central coordinating team at the NCTU using a specific SAE mailbox, [[contact]](mailto:[contact]). On receipt of the SAE, the central coordinating team will allocate the SAE a unique reference number, which will then be forwarded to the site as a proof of receipt within 1 working day. If confirmation is not received within 1 working day, the site should contact the NCTU office. The SAE reference number will be quoted on all correspondence and follow up reports regarding the SAE and filed with the actual SAE in the Site File and Trial Master File (TMF).

When an SAE form is completed someone other than Investigator, the Investigator will countersign the original SAE form to confirm agreement with the causality and seriousness assessments. The form should then be returned to NCTU and a copy kept in the Investigator Site File (ISF). The investigator should also report SAEs to their own Trust according to the local practice.

At the NCTU, SAEs on receipt will be reviewed independently by the Chief Investigator, who will be responsible to confirm the seriousness and causality assessment. If the causal relationship is either possibly, probably or definitely related with the trial IMP, this will be regarded as Serious Adverse Reaction (SAR). This SAR will be assessed by the CI for expectedness. If the SAR is unexpected (not defined in the RSI, see section 4.8 of the reference SmPC), it will be classified as a Suspected Unexpected Serious Adverse Reaction (SUSAR).

#### Non-expedited Serious Adverse Events:

Certain events, although they are, by definition classed, as Serious Adverse Events, are expected and will not require expedited reporting since a clinical assessment of expectedness is not required, but are still expected to be recorded in the clinical notes. In the context of this trial, this could be either:

- Adverse reaction from TCS use, requiring cessation of TCS;
- Active LS not controlled by rescue therapy, requiring escalation of therapy (either stepping up of TCS potency or moving to second-line immunosuppression);
- Suspicion of development of pre cancer/cancer of the vulva, requiring urgent action as per the recruiting sites usual process for investigating suspected malignancy.

All serious adverse events will be recorded and reported to the MHRA and REC as part of the annual Development Safety Update Reports (DSUR). SUSARs will be reported within the statutory timeframes to the MHRA and REC as stated below. The Sponsor shall ultimately be responsible for adverse event reporting.

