## 11 ADVERSE EVENTS

An adverse event is any unfavourable and unintended sign, symptom, syndrome or illness that develops or worsens during the period of observation in the study.

An AE includes:

1. Exacerbation of a pre-existing illness.
2. Increase in frequency or intensity of a pre-existing episodic event or condition.
3. Condition detected or diagnosed after medicinal product administration even though it may have been present prior to the start of the trial.
4. Continuous persistent disease or symptoms present at baseline that worsen following the start of the trial.

The interventions being evaluated in this trial are treatments that are widely available within the NHS and used in standard care for lichen sclerosus. Given the well-known safety profile of the interventions, we will adopt a targeted approach to AE reporting.

Reporting and follow-up of these targeted participant and investigator-reported complications associated with the intervention delivery will be recorded in trial e-CRFs in a structured format and do not need to be reported to the Research Ethics Committee (REC).

An AE does not include:

1. Medical or surgical procedure (e.g., surgery, endoscopy, tooth extraction, transfusion); but the condition that leads to the procedure is an AE.
2. Pre-existing disease or conditions present or detected at the start of the trial that did not worsen.
3. Situations where an untoward medical occurrence has not occurred (e.g. hospitalisations for cosmetic elective surgery, social and / or convenience admissions).
4. Disease or disorder being studied or sign or symptom associated with the disease or disorder unless more severe than expected for the participant's condition.
5. Overdose of concurrent medication without any signs or symptoms.

Although all AEs should be recorded in the medical notes, in accordance with GCP, only those AEs which are directly referred to in the e-CRF will be collected for this trial. However, where any AE event meets the criteria of an SAE (see section 11.2), it will require reporting on a SAE form by the PI or delegate.

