### 11.2 Serious Adverse Event (SAE)

SAE is any adverse event occurring following study mandated procedures, having received the IMP or placebo that results in any of the following outcomes:

1. Death
2. A life-threatening adverse event
3. Inpatient hospitalisation or prolongation of existing hospitalisation
4. A disability / incapacity
5. A congenital anomaly in the offspring of a participant

Important medical events that may not result in death, be life-threatening, or require hospitalisation may be considered a serious adverse event when, based upon appropriate medical judgment, they may jeopardize the patient or participant and may require medical or surgical intervention to prevent one of the outcomes listed in this definition

A distinction is drawn between serious and severe AEs. Severity is a measure of intensity whereas seriousness is defined using the criteria above. Hence, a severe AE need not necessarily be serious.

All reportable SAEs, must be assessed for causality by the PI or delegate.

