### **11.6 Notification of pregnancy**

If a pregnancy occurs in a participant who is in either arm of the trial, they will be withdrawn from the trial and should follow the direction of their GP regarding the pregnancy. Due to the low risk associated with the trial medications, no trial related adverse events in the mother or child are expected, therefore pregnancies and outcomes in withdrawn trial participants will not be actively monitored. However, all serious adverse events will be recorded and reported to the MHRA and REC as part of the annual DSUR. SUSARs will be reported within the statutory timeframes to the MHRA and REC as stated below. The Sponsor shall ultimately be responsible for adverse event reporting.

Current advice from the UK Tetralogy Information Service with regards to topical corticosteroids in pregnancy is that *'treatment should not be withheld if these products are indicated at any stage in pregnancy'*. European Guidelines (2023) [39] state that *'there is no objection to occasional use of TCS in genital LS (e.g. once or twice a week), however, potent TCS (e.g. mometasone furoate) are preferred to very potent TCS (clobetasol propionate) during pregnancy.'* The British Association of

Dermatologists Guidelines (2018) [14] state '*topical steroids can be safely continued during pregnancy and in the postdelivery period, if needed.*'

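### Section 11.5 declares steroid reactions that stop treatment and suspected vulval cancer expected in advance, against the protocol's own SAE and SUSAR rules, so an unlisted serious reaction could miss expedited reporting

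*Protocol*

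**What the plan says.** Under its sub-heading on non-expedited events, Protocol section 11.5 sets apart certain events that it regards as serious by definition. They "are expected and will not require expedited reporting since a clinical assessment of expectedness is not required". On how they are to be documented, the sub-section adds of these events: "but are still expected to be recorded in the clinical notes". Three categories follow. The first is "Adverse reaction from TCS use, requiring cessation of TCS". The second is active disease that rescue therapy does not control and that needs escalation. The third is "Suspicion of development of pre cancer/cancer of the vulva, requiring urgent action". The sub-section ends by saying that all SAEs go into the annual Development Safety Update Report (DSUR) and that SUSARs are reported on the statutory timelines.

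The general rules are elsewhere in section 11:

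- **Section 11, opening text.** When any adverse event meets the SAE criteria, "it will require reporting on a SAE form by the PI or delegate".
- **Section 11.1.** Known side effects are spared expedited reporting only when they are not serious.
- **Section 11.5, main text.** Sites notify the coordinating centre of any SAE within 24 hours. An SAE that is possibly, probably or definitely related is a serious adverse reaction (SAR). "This SAR will be assessed by the CI for expectedness", the reference being SmPC section 4.8. A SAR not found there is a SUSAR.
- **Section 11.8.** Suspected SUSARs are handled as SUSARs until a decision to the contrary, and the Chief Investigator assesses seriousness, expectedness and relatedness.

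**The concern.** Expectedness of a serious reaction is decided case by case against a reference document. The sub-section decides it in advance for whole categories, and the first of these is a drug reaction defined by its consequence (the steroid was stopped), not by its nature. Such a category takes in listed and unlisted reactions alike.

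At stake is prompt regulatory and ethics review of an unexpected serious reaction, in a trial that enrols children from age 5 and has long-term steroid safety as its third secondary objective. Site staff and the Chief Investigator also have two incompatible instructions for the same event and no statement of which prevails.

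**Working it through.** No arithmetic applies. The check sets the rules side by side and asks what each requires of the same event.

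**Step 1. Scope of the waiver.** The first category is by its wording caused by the study drug, so a serious case is a related SAE. It is not restricted to reactions in the exemplar SmPCs that section 2.7 names as reference safety information. The third category is not restricted by relatedness at all.

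**Step 2. One event under both sets of rules.** Take a serious TCS reaction that leads to stopping the steroid and is not in SmPC section 4.8.

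| Question | Section 11.5, non-expedited events | Sections 11, 11.1, 11.5 main text and 11.8 |
|---|---|---|
| Is expectedness assessed? | No, it is taken as expected | Yes, by the Chief Investigator |
| Default status | Expected | SUSAR if suspected, pending a decision |
| Expedited reporting? | No | Yes |
| Record asked for | Clinical notes, then DSUR | SAE form, centre told within 24 hours |

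Section 11.8 gives anaphylaxis as its example of a sudden-onset event. Anaphylaxis attributed to the steroid, with the steroid stopped, falls in both columns.

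**Step 3. Suspected vulval cancer.** The known reactions in section 2.6 do not include vulval pre-cancer or cancer. Section 11.4 does list pre-cancerous change among the targeted events, but not invasive cancer. If a case were serious and judged at least possibly related, the main text of 11.5 would require an expectedness assessment and the sub-section would waive it. The SmPCs are not at hand, so what section 4.8 lists is unverified. The conflict does not depend on it, because the waiver removes the comparison with section 4.8 whatever that section contains.

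**Step 4. Does the closing sentence on SUSARs repair this?** No. In the main text of 11.5 a SAR becomes a SUSAR only when it is found to be unexpected, and in 11.8 the Chief Investigator again has to judge expectedness. An event whose expectedness is never assessed does not reach the statutory timeline by that route.

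**Step 5. Which kind of expediting is meant?** The sub-section does not say whether it concerns the site's 24-hour notice or the report to regulator and ethics committee. On the first reading it conflicts with the SAE form and 24-hour rules as well as the expectedness rule. On the second, the conflict over expectedness remains. Section 11.1 is against either reading for serious events, since it makes its own exemption conditional on the event not being serious.

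**The case against.** The best defence is that the sub-section was meant only to stop sites rushing through reports of anticipated, disease-related events. Section 11.2 speaks of reportable SAEs, which hints that a non-reportable class was intended. Section 11.8 presumes SUSAR status in cases of doubt, and the main text of 11.5 states no exception to the 24-hour notice. A careful Chief Investigator would probably follow those rules. This limits the likely harm, but the text does not state the narrower intention, and a drug reaction heads the list.

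The defence does defeat several stronger readings that a reader might infer:

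- **That these events would exist only in clinical notes, or go wholly unreported.** The sub-section asks for clinical-note recording but does not say only, and it keeps every SAE in the DSUR.
- **That the coordinating centre and Data Monitoring Committee would not see them.** Section 11.4 collects pre-cancerous change, hypersensitivity and many steroid reactions on the e-CRF. Table 7 records change or cessation of therapy at each follow-up visit. Section 5.1 has the site's principal investigator inform the centre of suspected cancer raised by a blinded assessor. Section 10.3 gives the committee safety reports by arm.
- **That VIN and vulval SCC are looked for only at 24 months, as one row of Table 7 might suggest.** Table 2 collects them over 24 months from clinical assessment and notes.
- **That the three categories cannot be SAEs because stopping or escalating treatment is not in the numbered list of 11.2.** That section also has a medical-judgement clause through which they could qualify.
- **That section 11.6 contradicts 11.2 on pregnancy.** Section 11.2 counts "A congenital anomaly in the offspring of a participant" as an SAE, while 11.6 says "pregnancies and outcomes in withdrawn trial participants will not be actively monitored". This is a stated choice of passive follow-up with reasons given, and 11.6 goes on to keep SAE reporting in force.

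**Conclusion.** The contradiction stands. For TCS reactions leading to cessation and for suspected vulval pre-cancer or cancer, one part of section 11.5 waives an expectedness assessment that the main text of 11.5 and section 11.8 require for related serious events. It also sits against the SAE form rule in section 11 and the non-serious condition in 11.1. The consequence is confined to classification and timing: a serious related reaction outside the reference safety information could fail to be classified and expedited as a SUSAR. It should still appear in the DSUR and may be captured as a targeted adverse event or outcome.

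Two of the three listed categories are affected, and one of them is drug-related by its own wording. The protocol gives no expected event numbers, so no frequency can be attached. The conclusion assumes that someone applies the sub-section as written in preference to the general rules. It does not touch the primary comparison or its analysis. It is worth correcting because it concerns participant safety and the correction is cheap.

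**What to change.** Reconcile the sub-section on non-expedited events with section 11, section 11.1, the main text of 11.5 and section 11.8. State that:

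1. any event meeting section 11.2, including one in the three listed categories, goes on an SAE form within 24 hours;
2. if it is judged related, the Chief Investigator assesses expectedness against the reference safety information in section 2.7;
3. a listed event that does not meet 11.2 is recorded in the e-CRF.

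Remove the advance declaration that the listed events are expected, and the description of them as SAEs by definition. No treatment rule, visit or analysis changes. The cost is an amendment to the wording of section 11.5 and a few more SAE forms for sites.

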### **11.6 Notification of pregnancy**

If a pregnancy occurs in a participant who is in either arm of the trial, they will be withdrawn from the trial and should follow the direction of their GP regarding the pregnancy. Due to the low risk associated with the trial medications, no trial related adverse events in the mother or child are expected, therefore pregnancies and outcomes in withdrawn trial participants will not be actively monitored. However, all serious adverse events will be recorded and reported to the MHRA and REC as part of the annual DSUR. SUSARs will be reported within the statutory timeframes to the MHRA and REC as stated below. The Sponsor shall ultimately be responsible for adverse event reporting.

Current advice from the UK Tetralogy Information Service with regards to topical corticosteroids in pregnancy is that *'treatment should not be withheld if these products are indicated at any stage in pregnancy'*. European Guidelines (2023) [39] state that *'there is no objection to occasional use of TCS in genital LS (e.g. once or twice a week), however, potent TCS (e.g. mometasone furoate) are preferred to very potent TCS (clobetasol propionate) during pregnancy.'* The British Association of

Dermatologists Guidelines (2018) [14] state '*topical steroids can be safely continued during pregnancy and in the postdelivery period, if needed.*'

### 11.7 Urgent Safety Measures

Definition of Urgent Safety Measures and reporting is described on section 8.6.

### 11.8 SUSARs

A serious adverse event that is either sudden in its onset (anaphylaxis), unexpected in its severity and seriousness or not a known side effect of the IMP *and* related or suspected to be related to the IMP is classed as Suspected Unexpected Serious Adverse Reaction and requires expedited reporting as per the clinical trials regulations.

All serious adverse events that fall or are suspected to fall within these criteria shall be treated as a SUSAR until deemed otherwise.

The event shall be reported immediately (within 24 hours) of knowledge of its occurrence to the Chief Investigator.

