### 11.1 Reference Safety Information:

The known side effects are events that do not require expedited reporting (providing they do not meet the criteria of an SAE), but will be collated on the e-CRFs, have been taken from the exemplar

Summary of Product Characteristics, sections 4.8 of Dermovate ointment and Elocon ointment, and are detailed in this protocol section 11.4.

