### 11.3 Causality

**Not related or improbable:** a clinical event including laboratory test abnormality with temporal relationship to trial treatment administration which makes a causal relationship incompatible or for which other drugs, chemicals or disease provide a plausible explanation. This will be counted as "unrelated" for notification purposes.

**Possible:** a clinical event, including laboratory test abnormality, with temporal relationship to trial treatment administration which makes a causal relationship a reasonable possibility, but which could also be explained by other drugs, chemicals or concurrent disease. This will be counted as "related" for notification purposes.

**Probable:** a clinical event, including laboratory test abnormality, with temporal relationship to trial treatment administration which makes a causal relationship a reasonable possibility, and is unlikely to be due to other drugs, chemicals or concurrent disease. This will be counted as "related" for notification purposes.

**Definite:** a clinical event, including laboratory test abnormality, with temporal relationship to trial treatment administration which makes a causal relationship a reasonable possibility, and which can definitely not be attributed to other causes. This will be counted as "related" for notification purposes.

An AE whose causal relationship to the trial IMP is assessed by the PI or Medical Monitor as “possible”, “probable”, or “definite” is an Adverse Drug Reaction.

With regard to the criteria above, medical and scientific judgment shall be used in deciding whether prompt reporting is appropriate in that situation.

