#### **11.4 Reporting of adverse events**

Targeted adverse events will be recorded and closely monitored until resolution, stabilisation, or until it has been shown that the trial medication or treatment is not the cause.

In the PEARLS trial these targeted AEs are:

- Progression of scarring
- Pre-cancerous changes to the anatomy
- Infection (thrush and superficial bacterial infection)
- Hypersensitivity, generalised rash
- Cushing’s syndrome
- Local skin burning/skin pain and pruritus
- Allergic/contact dermatitis, erythema, rash, urticaria, local atrophic changes in the skin such as thinning, skin wrinkling, skin dryness, striae and dilatation of the superficial blood vessels (telangiectasias) may be caused by prolonged and intensive treatment with highly active corticosteroid preparations, particularly when occlusive dressings are used or when skin folds are involved.

Sites should report these events via e-CRFs.

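### Sections 11.5 and 11.8 of the protocol define a SUSAR by different tests, and the non-expedited list in 11.5 exempts reactions that 11.8 would expedite

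*Protocol*

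**What the plan says.** Three rules in section 11 of the protocol bear on whether a related serious event is expedited.

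- **Section 11.5, main text.** An SAE rated possibly, probably or definitely related is a serious adverse reaction (SAR). "This SAR will be assessed by the CI for expectedness". The criterion follows: "If the SAR is unexpected (not defined in the RSI, see section 4.8 of the reference SmPC"). A SAR that meets it is classified as a SUSAR.
- **Section 11.5, non-expedited list.** Some SAEs are declared expected and are not expedited, on the ground that their expectedness need not be assessed. One of the three categories is a reaction to the TCS that leads to its being stopped.
- **Section 11.8.** A related or possibly related SAE is a SUSAR if it is "either sudden in its onset (anaphylaxis), unexpected in its severity and seriousness or not a known side effect of the IMP". Any event that meets or may meet these criteria "shall be treated as a SUSAR until deemed otherwise". The Chief Investigator assesses seriousness, expectedness and relatedness. For a SUSAR, the individual case report and the notice to the ethics committee are each due within seven days.

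**The concern.** Expectedness decides whether a related serious event is reported within days or appears only in the annual safety report. The protocol gives more than one rule for that decision, and no text says which prevails.

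Two groups of events are exposed. The first is listed reactions that turn out worse than the RSI describes. The second is reactions serious enough that the TCS is stopped. Both matter in a trial with 24 months of treatment in participants from age 5, whose protocol (section 2.6) concedes that the risk of adverse effects of TCS is poorly quantified. Two people applying the protocol faithfully, one from 11.5 and one from 11.8, could give opposite answers on the same statutory report.

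**Working it through.** No arithmetic applies. The check takes each rule as written and applies it to the same events.

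**Criteria side by side**

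| Feature of a related SAE | 11.5 main text | 11.5 non-expedited list | 11.8 |
|---|---|---|---|
| Not in the RSI, or not a known side effect | SUSAR | Not considered | SUSAR |
| Listed, but severity and seriousness unexpected | Not mentioned | Not considered | SUSAR |
| Sudden onset (anaphylaxis) | Not mentioned | Not considered | SUSAR |
| TCS reaction that led to stopping TCS | Not mentioned | Expected, not expedited | Not mentioned |
| Chief Investigator assesses expectedness | Yes, for every SAR | Not required | Yes |

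Only the first row is common ground between the main text of 11.5 and 11.8.

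**Test cases, each rated possibly related**

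| Case | 11.5 main text | 11.5 list | 11.8 |
|---|---|---|---|
| A. Listed reaction, severity judged unexpected, TCS continued | Not a SUSAR | Does not apply | SUSAR |
| B. As A, but TCS stopped because of it | Not a SUSAR | Exempt | SUSAR |
| C. Anaphylaxis, TCS stopped because of it | Depends on SmPC section 4.8, which the protocol does not reproduce | Exempt | SUSAR |
| D. Reaction not in the RSI, TCS stopped because of it | SUSAR | Exempt | SUSAR |
| E. Listed reaction, expected severity, gradual onset, TCS continued | Not a SUSAR | Does not apply | Not a SUSAR |

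**Reading the cases**

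1. Case A is the direct conflict between the two definitions. An example is a skin infection that leads to admission. Infection is among the known reactions that section 2.6 takes from the SmPC, so the main text of 11.5 makes it expected. Section 11.8 makes it a SUSAR if its severity is judged unexpected. If its severity is judged expected, the sections agree, as in case E.
2. Case C shows the conflict through the list. Whatever the SmPC says about anaphylaxis, the list exempts it once the TCS is stopped for it, while 11.8 names it as an example of a SUSAR.
3. Case D shows that 11.5 contradicts itself. Its main text sends every SAR to the Chief Investigator for expectedness and makes this one a SUSAR. Its list says that no such assessment is needed and exempts the same event.

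**The case against.** The strongest defence is that 11.8 is the dedicated SUSAR section. Section 11.5 refers forward to it for SUSAR reporting, and its precautionary default covers any event that may meet the criteria. An experienced safety assessor would probably also read severity into the RSI test. Every SAE still reaches the regulator and the ethics committee in the annual report.

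This lowers the risk of a missed report but does not remove the conflict. The forward reference concerns timeframes and does not say that 11.8 overrides the definition or the list in 11.5. The default lasts only until somebody decides, and that person then has two criteria to choose from. An annual report does not replace an expedited one.

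A reader might infer three stronger points that the protocol does not support:

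- **That section 11.1 is a third test, under which every serious listed reaction is expedited.** It describes known side effects as "events that do not require expedited reporting (providing they do not meet the criteria of an SAE"). It thus exempts non-serious events and leaves the classification of serious ones to later sections.
- **That the RSI test makes anaphylaxis expected, because section 11.4 lists "Hypersensitivity, generalised rash".** Section 11.1 does link the 11.4 list to the SmPCs. But 11.4 is the list of targeted events and also holds progression of scarring and pre-cancerous changes. Section 2.6 names neither hypersensitivity nor anaphylaxis, and the SmPC text is not shown. If anaphylaxis is absent from section 4.8, the RSI test and 11.8 agree on it.
- **That the roles conflict.** In section 11.3 causality is "assessed by the PI or Medical Monitor", and in 11.5 the event goes to the Chief Investigator, "who will be responsible to confirm the seriousness and causality assessment". That is a site assessment followed by central review, which is a sequence and not a contradiction. The protocol shows no conflict here that would call for a rule on whose rating counts.

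**Conclusion.** The point holds for the relation between 11.5 and 11.8 and for the non-expedited list. A listed reaction of unexpected severity is a SUSAR under 11.8 and not under the wording of 11.5. A reaction that leads to stopping the TCS, including anaphylaxis, is exempt under the list even where 11.8, or the main text of 11.5 itself, makes it a SUSAR.

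The conclusion rests on the wording alone and on the absence of any statement of precedence. For anaphylaxis it rests on the list, not on the RSI test. How many events would be affected cannot be estimated from the protocol. This is a safety-reporting inconsistency with no bearing on the sample size, randomisation or primary analysis. It should be corrected, because it decides which serious reactions are expedited and costs little to put right.

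**What to change.** Reconcile the main text of 11.5, its non-expedited list and 11.8 to one definition, used in both sections: a SUSAR is an SAE rated possibly, probably or definitely related whose nature or severity is not consistent with section 4.8 of the RSI SmPC.

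Then:

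1. Replace the parenthesis in 11.5 and the three alternatives in 11.8 with that definition. If anaphylaxis is kept as an example, check it against section 4.8 of both SmPCs named in section 2.7.
2. State that the non-expedited list does not exempt an event that meets the definition.
3. Remove from the list the statement that expectedness need not be assessed, so that it agrees with the Chief Investigator's task in 11.5 and 11.8.

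The cost is a change of protocol wording and of any matching SAE instruction. The downside is possibly a few more expedited reports. Treatment, design and analysis stay as they are.
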